5.7. Intervention

1) Control group: immediate antibiotic prescription. We wish to provide some estimate of the reduction in antibiotic possible compared with current practice. Since more than 90% of patients currently receive antibiotic for acute sinusitis the nearest approximation to usual care is a prescription for immediate antibiotics, combined with advice about the use of analgesics. Although the particular antibiotics used is not the focus of this investigation, in line with PHE guidance for primary care we will advise the use of Penicillin V 500mgs QDS (or alternatively Amoxicillin 500mg tds) for 1 week or Clarithromycin 500mg BD also for 1 week if participants are allergic to penicillin.

2) Advice to use nasal irrigation. In addition to the advice in the usual care arm to use simple analgesics participants will be given both written and verbal instructions and given a link to a video clip (uploaded on YouTube: http://www.youtube.com/watch?v=zgvoxkGYSU4) demonstrating how to perform irrigation. They will be asked to irrigate the nose (150 ml through each nostril) daily for up to 21 days or until symptoms settle, and a SinuCleanse 19 nasal cup ('Netipot') will be provided to each subject. Patients will make their own buffered saline irrigation solution every 1 to 2 days comprising: 1 heaped teaspoon salt, one half teaspoon baking soda and 1 pint (568 ml) tap water; how to do this will also demonstrated on the video clip. We chose this particular intervention based on the provisional evidence from a previous randomised controlled trial in primary care in chronic/recurrent sinusitis (11) and from our most recent large trial also in chronic or recurrent sinusitis (13), where most patients found it acceptable and the majority continued using nasal irrigation. Participants in this group will be offered a delayed antibiotic prescription as in our previous trials(19), and advised only to use it if symptoms are getting significantly worse or not even starting to settle a little after a further week.

All study participants in both groups will have access to usual care; further medication or referral will be at the discretion of the doctor according to the normal practice of that doctor.

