- Duration of moderately bad illness. The duration of illness rated moderately bad or worse i.e. making an important difference to patients, and as used in our previous studies of respiratory infections (20, 21). It will be measured using the symptom diary and where the diary is not returned information from a brief follow-up questionnaire, and/or phone call as necessary. The 4 week diary includes 11 symptom variables, assessed on 7 point Likert scales. The score has been developed to have content validity by incorporating items which not only take account of proposed diagnostic criteria for bacterial rhinosinusitis(22) but also physicians' perceptions of the important clinical features (based on focus groups and a questionnaire study)(23). The format of the diary items has been developed in a variety of other respiratory infections and been shown to have construct and criterion validity, and also sensitivity to change.(8, 17, 24) We have also shown the total symptom score for sinusitis is internally reliable (Cronbach's alpha 0.77) and sensitive to change (standardized response mean 1.6 comparing day 0 with day 5).(8, 24)
- The duration of any symptom until rated very little or no problem (measured as above);
- **Reconsultation** with non-resolving, new, or worsening illness within 1 month of the index consultation documented from medical records, and which can be measured reliably(25);
- EQ5D5L (at days 1,7,14,21,28 of the diary). In prior trials EQ5D has been shown to be adequate in detecting the decrement in QOL with RTIs to allow cost-effectiveness modelling(26) should the main trial be funded;
- **Resource use.** Information on NHS resource usage will be collected for all participants from a notes review including capturing resource use for rare major adverse events (e.g. anaphylaxis, complications, hospital admission) up to 28 days.

- Self-reported adherence and reasons for non-adherence, using the validated Problematic Experiences of Therapy Scale, across different aspects of intervention materials (written / video / online instructions).
- Modified Patient Enablement Instrument(27)

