5.15. Sample size calculation

Feasibility estimates: to estimate follow-up rates between 65% and 80% assuming we want to be reasonably sure that the follow-up rate is not 50% in each group (i.e.95% confidence intervals of +/- 15%) then 41 per group are needed. We anticipate that it should be possible for the intervention group to achieve use of antibiotics of around 65% or less. To estimate this proportion with 95% confidence intervals of +/- 15% (i.e. to be sure the use of antibiotics is 80% or less) 41 per group is also needed.

Provisional estimates of antibiotic reduction. In addition to descriptive information of antibiotic in each group we can also provide very provisional estimates of the difference in antibiotic use compared with control: 43 individuals per group will detect a plausible 25% absolute reduction in antibiotic use (for alpha=0.05 and 80% power) to 65% assuming at least 90% of the control group use antibiotics. Allowing for 20% loss to follow-up we will recruit 108 participants.

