7. SAFETY REPORTING

All adverse events, for patients randomised into the trial, should be reported from the time the patient signs the informed consent form until one week after randomisation. Depending on the nature of the event the reporting procedures below should be followed.

Any questions concerning adverse event reporting should be directed to the Study coordination centre in the first instance. A flowchart will be provided to aid in the reporting procedures.

Adverse events presenting to the participants GP will be notified by the practitioner. In addition participants will carry a study card which highlights the need to notify their own doctor regarding adverse events. As a final check all participants will be asked to consent to a medical notes review which will take place after study recruitment at a time when any letters will have been returned from out-patient appointments. This enables us to be confident of detecting adverse events which have not been notified using the first two mechanisms. A member of the research team will provide the practice staff with instructions for extraction of data and a form to record the data from participants' medical notes on further antibiotics and other medications prescribed during the 28-day period after study entry.

Adverse Event (AE)	Any untoward medical occurrence in a participant to whom a		
	medicinal product has been administered, including occurrences		
	which are not necessarily caused by or related to that product.		
	These will not be collected for this study.		
Adverse Reaction (AR)	An untoward and unintended response in a participant to an		
	investigational medicinal product which is related to any dose		
	administered to that participant.		
	The phrase "response to a trial intervention" means that a causal		
	relationship between a trial intervention and an AE is at least a		
	reasonable possibility, i.e. the relationship cannot be ruled out. All		
	cases judged by either the reporting medically qualified professional		
	or the Sponsor as having a reasonable suspected causal		
	relationship to the trial qualify as adverse reactions.		
Serious Adverse Event	A serious adverse event is any untoward medical occurrence that:		
(SAE)	results in death		
	is life-threatening		
	 requires inpatient hospitalisation (i.e an overnight stay) or 		
	prolongation of existing hospitalisation		
	 results in persistent or significant disability/incapacity 		

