7.7. Safety Monitoring Committee

The Trial Steering Committee will be responsible for reviewing SAEs after each recruitment season. The main aims of this review are as follows:

- To ensure the safety of each patient in the trial;
- To pick up any trends, such as increases in unexpected events, and take appropriate action;
- To seek additional advice or information from investigators where required;

• To evaluate the risk of the trial continuing and take appropriate action where necessary;

• To act or advise, through the Chairman or other consultant, on incidents occurring between meetings that require rapid assessment.

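### The one-week adverse event reporting window covers the immediate antibiotic course but little of a delayed course, and as few as 7 of up to 21 irrigation days

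*Protocol*

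**What the plan says.** **Reporting window.** The opening of section 7 says that all adverse events in randomised patients "should be reported from the time the patient signs the informed consent form until one week after randomisation". It then directs the reader to the procedures below according to the type of event. Sections 7.4 to 7.6 (SAE reporting, expectedness, SUSARs) give no end date of their own.

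**Treatment periods (section 5.7).** Controls get an antibiotic prescription at once, for a week whichever drug is used ("for 1 week or Clarithromycin 500mg BD also for 1 week"). The intervention arm irrigates "daily for up to 21 days or until symptoms settle". It also receives a delayed prescription and is "advised only to use it if symptoms are getting significantly worse or not even starting to settle a little after a further week".

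**Other routes by which harms are captured.**
- The diary runs for up to four weeks (5.11). Section 7.3 makes it the sole source for side effects of interest.
- Section 7 describes notification by the GP, a study card carried by the participant, and a notes review as a last check for events missed by these two. The data form described there, and in 6.5, is for antibiotics and other medications over 28 days.
- The resource-use item in 5.12 provides for "capturing resource use for rare major adverse events (e.g. anaphylaxis, complications, hospital admission) up to 28 days".
- Section 7.4 and Appendix E start the 24-hour clock when someone becomes aware of an SAE.

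**Oversight.** Section 7.7: "The Trial Steering Committee will be responsible for reviewing SAEs after each recruitment season".

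**What is collected.** The definitions table in section 7 states that adverse events are not gathered in this study. This conflicts with the instruction to report all of them for a week.

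**The concern.** A reporting window should span the period in which participants are exposed to the treatments under study. This one matches the control arm's antibiotic course almost exactly. It closes at about the time the intervention arm's delayed prescription becomes due under the rule "not even starting to settle a little after a further week", and while irrigation may still have two weeks to run.

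Section 7 says that the trial will gather data on anaphylaxis, severe allergy treated with steroids, emergency admission with chest problems and severe Clostridium diarrhoea. A site that applies the one-week sentence to these need not report one that occurs on days 8 to 28. The Trial Steering Committee's seasonal SAE review, and any advice on termination under 7.9, could then rest on different fractions of antibiotic exposure in the two arms. A site that reads 7.4 as open-ended would report the same event, so sites could work to different windows.

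**Working it through.** The one-week window is a stated rule with no calculation behind it, so the check compares it with the treatment periods by day count. Day 0 is randomisation.

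**Inputs**
- Reporting window after randomisation: 7 days (section 7).
- Immediate course: days 0 to 7 (5.7).
- Irrigation: L days, at most 21, fewer if symptoms settle (5.7).
- Delayed course: starts on day s, at about day 7 for non-settling symptoms, earlier for marked worsening (5.7). Its length is assumed to be 7 days, as for the control course.
- Diary and notes-review horizon: 28 days (5.11, 5.12, 6.5).

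**Immediate course.** Share inside the window = 7/7 = 100%.

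**Delayed course.** Share inside = max(0, 7 − s)/7.

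| Start day s | Share inside the window |
|---|---|
| 3 | 4/7 = 57% |
| 5 | 2/7 = 29% |
| 7 or later | 0% |

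The protocol does not say how many would start early. Suppose that a fraction f of delayed users starts on day 3 and the rest on day 7 or later (an assumption). The covered share of antibiotic days is then f × 4/7: 0% for f = 0, 14% for f = 0.25 and 29% for f = 0.5. The immediate arm has 100%.

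**Irrigation.** Share outside = 1 − min(7, L)/L.

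| Irrigation length L (days) | Share outside the window |
|---|---|
| 7 | 0% |
| 10 | 3/10 = 30% |
| 14 | 7/14 = 50% |
| 21 | 14/21 = 67% |

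Section 3 cites a median illness of 2 weeks in a UK primary care trial and nearly 3 weeks in a systematic review. The starting point of these durations is not stated, but irrigation past day 7 is plausible for many participants.

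**Number of people concerned.** Section 5.15 plans 108 participants, so 54 per arm if the arms are equal. It expects at least 90% antibiotic use in controls: 54 × 0.90 = 48.6, about 49 users. For the intervention arm it says that "it should be possible for the intervention group to achieve use of antibiotics of around 65% or less": 54 × 0.65 = 35.1, so about 35 users or fewer.

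**With a 28-day window.** It would cover 21/21 irrigation days, the whole immediate course, and all of a 7-day delayed course started by day 21 (21 + 7 = 28).

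**The case against.** The strongest reply is that the one-week sentence is not the only safety net. Section 7 itself describes GP notification, a study card and a notes review intended to find events not otherwise notified. The four-week diary applies in both arms. Section 7.4 and Appendix E run from awareness of an SAE, with no stated end, and Appendix E lets a study team member start the form. On that reading, an SAE found in the notes would enter the 24-hour and SUSAR route, and the Committee would not be confined to first-week events. Section 11 also has it reviewing accruing data after each winter.

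Much of this stands. It rules out saying that late harms go uncaptured. It does not remove the conflict:
- the notes-review form is described for medications;
- the 28-day capture of major events is framed as resource use;
- the diary may be posted back once symptoms settle and is not an SAE route;
- nothing says that 7.4 overrides the one-week limit.

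A reader might also infer that the window makes the intervention arm look safer by design. The documents do not support this. Full coverage of a control's antibiotic days is not full coverage of reactions, because those starting after day 7 are missed in controls too. The first week also picks up early irrigation effects and early worsening, which count against the intervention arm.

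Nor can a number of missed events be given. The protocol states no rate for reportable events, and common antibiotic reactions that are non-serious and mild to moderate need no report form.

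Finally, this is a pilot in which comparative harm is not a listed outcome. That bears on severity, not on whether the text needs correcting.

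**Conclusion.** The mismatch is real and of moderate severity. On its natural reading, section 7 limits reporting, including the SAE procedures it leads into, to one week. That covers all of the immediate antibiotic course, none of a delayed course started on day 7 or later, and as little as a third of the irrigation period.

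The 67% is a maximum, because irrigation stops when symptoms settle. The 0% applies to the non-settling rule; if up to half of delayed users began on day 3, coverage would be at most 29%. These figures assume a 7-day delayed course.

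The unequal coverage belongs to the section 7 reporting route, not to all harm data, and the direction of any resulting bias is not established. The contradiction over whether adverse events are collected belongs to the same point, because lengthening the window alone would extend a duty that the same section denies. The antibiotic-use outcome, follow-up and sample size are unaffected.

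**What to change.** Amend section 7 and the linked text together:

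1. State one reporting window, from consent to 28 days after randomisation, the same in both arms, for SAEs and for the severe reactions named in section 7. This is the protocol's own diary and notes-review horizon.
2. State that sections 7.4 to 7.6 apply throughout that window, and that an SAE first found at the notes review goes through the same form and timelines, so that the Trial Steering Committee sees it. Add adverse events to the notes-review form described in section 7.
3. Reconcile the three statements on non-serious events: that all are reported for a week, that none are collected, and that side effects come from the diary alone. Say which events are collected, by which route and for how long.

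The cost is an amendment to several linked passages and a few more SAE forms from 108 participants. No new visits are needed, because the diary and notes review already run to 28 days, and the sample size does not change. A 7-day course started after day 21 would still run past the window; the amendment should acknowledge this.

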7.1. Definitions

NB: to avoid confusion or misunderstanding of the difference between the terms "serious" and "severe", the following note of clarification is provided: "Severe" is often used to describe intensity of a specific event, which may be of relatively minor medical significance. "Seriousness" is the regulatory definition supplied above.

7.2. Causality

The relationship of each adverse event to the trial intervention must be determined by a medically qualified individual according to the following definitions:

Related: The adverse event follows a reasonable temporal sequence from trial intervention. It cannot reasonably be attributed to any other cause.

Not Related: The adverse event is probably produced by the participant's clinical state or by other modes of therapy administered to the participant.

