	 consists of a congenital anomaly or birth defect. 		
	Other 'important medical events' may also be considered serious if		
	they jeopardise the participant or require an intervention to prevent		
	one of the above consequences.		

	NOTE: The term "life-threatening" in the definition of "serious" refers	
	to an event in which the participant was at risk of death at the time	
	of the event; it does not refer to an event which hypothetically might	
	have caused death if it were more severe.	
Serious Adverse Reaction	An adverse event that is both serious and, in the opinion of the	
(SAR)	reporting Investigator, believed with reasonable probability to be due	
	to the trial treatments, based on the information provided.	

Hospitalisations for elective treatment of a pre-existing condition do not need reporting as Serious Adverse Events (SAEs).

The antibiotics used in SNIFSII (beta-lactams or macrolides) are licensed medicines whose most common side-effects are mucocutaneous candidosis (thrush), diarrhoea, nausea, vomiting and rash (occurrence >=1/100 to <1/10). If these occur and are non-serious and of mild to moderate severity (based on clinician's assessment) an Adverse Event Report form will not be necessary. We will collect data on events such as severe reactions to the antibiotics such as anaphylaxis, severe allergy requiring steroid administration, emergency hospitalization for chest problems and severe Clostridium (antibiotic related diarrhoea).

Unexpected adverse reactions to antibiotics will be highly unlikely amongst trial participants, as the vast majority of patients will have previously received antibiotics to treat other infections. For non-serious adverse reactions to trial medication, the Chief Investigator or a designated alternative study clinician will assess the urgency with which the participant's treatment allocation should be unblinded.

For Nasal Irrigation there have been no serious sides effects reported, the most common side effects being nasal stinging and sinus discomfort for some patients.

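### Sections 7 and 7.2 set three conflicting causality thresholds, so a serious event with a possible link to treatment and another plausible cause may miss expedited SUSAR reporting

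*Protocol*

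**What the plan says.** Four places in the Protocol bear on whether an event counts as caused by the trial intervention.

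- **Section 7, Adverse Reaction row.** The causal relationship has to be at least a "reasonable possibility, i.e. the relationship cannot be ruled out". The judgement may come from the reporting medically qualified professional "or the Sponsor as having a reasonable suspected causal" relationship to the trial.
- **Section 7, Serious Adverse Reaction row.** The event must be serious and, in the opinion of the "reporting Investigator, believed with reasonable probability to be due" to the trial treatments. The Sponsor is not mentioned here.
- **Section 7.2, Causality.** The relationship of each adverse event "must be determined by a medically qualified individual according to the following definitions". There are two categories. Related needs a reasonable temporal sequence and adds: "It cannot reasonably be attributed to any other cause". Not Related reads: "The adverse event is probably produced by the participant's clinical state or by other modes of therapy administered to the participant".
- **Section 7.4 and Appendix E.** Section 7.4 sends every serious adverse event to the coordinating centre within 24 hours and has the Chief Investigator or a representative assess expectedness for those reported as related to the trial. Appendix E has the Chief Investigator or a safety delegate check seriousness, relatedness and expectedness, with the option of upgrading the event.

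**The concern.** The same judgement is defined three ways, and the definitions cannot all be followed. The Adverse Reaction row is inclusive: doubt counts as a reaction. Section 7.2 is exclusionary: a reasonable alternative explanation is enough to defeat Related. The Serious Adverse Reaction row uses a third phrase, and how it sits against the other two is not explained.

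This matters because the causality class acts as a gate. Under Section 7.4 expectedness is assessed for serious events reported as related. An event becomes a SUSAR only if it is found unexpected, and the 7-day and 15-day reports to the ethics committee in Section 7.6 apply only to SUSARs. The strictest of the three definitions is also the one that 7.2 makes compulsory. An assessor who follows the text faithfully could therefore keep out of the expedited route an event that Section 7 itself calls a reaction.

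Such events are foreseeable. Section 7 names emergency admission for chest problems among the events of interest. In a patient with a respiratory infection, such an admission could have another reasonable cause even where a link to treatment cannot be excluded.

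**Working it through.** The protocol gives no figure to reproduce and no arithmetic applies. The check takes the definitions as written, applies each to the possible kinds of serious event, and follows the result through the reporting route.

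**Step 1. Conditions.**

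- Adverse Reaction (Section 7): a link is at least reasonably possible.
- Serious Adverse Reaction (Section 7): the reporting investigator believes a link reasonably probable.
- Related (7.2): the timing fits and no other reasonable cause exists.
- Not Related (7.2): another cause is probable.

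**Step 2. Three kinds of serious event, each with plausible timing and a link that cannot be ruled out.**

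| Kind | Other cause | Adverse Reaction row | Serious Adverse Reaction row | Section 7.2 |
|---|---|---|---|---|
| (a) | none that is reasonable | reaction | likely met | Related |
| (b) | probable | reaction | likely not met | Not Related |
| (c) | reasonable, not probable | reaction | unclear | neither category |

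Kind (a) is consistent throughout. Kind (b) is a direct contradiction: a reaction in Section 7 and Not Related in 7.2. Kind (c) is a gap: the alternative cause is strong enough to defeat Related but not strong enough to satisfy Not Related. Under kind (b) an event can also be serious and an adverse reaction without meeting the Serious Adverse Reaction row, which should not be possible if the rows are meant to nest.

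**Step 3. The reporting route.**

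1. All serious events reach the coordinating centre within 24 hours (7.4), whatever their causality class.
2. Expectedness is assessed for those reported as related (7.4). Kind (b) is not so reported. Kind (c) cannot properly be so reported, since it fails Related.
3. SUSAR status needs expectedness to have been assessed. Without it, the 7-day and 15-day reports in 7.6 are not triggered.
4. Appendix E provides a second look at relatedness and expectedness and allows an upgrade. It contains no causality definition of its own, so the person rechecking is left with the same conflicting texts, of which 7.2 is the one stated as mandatory.
5. The Trial Steering Committee reviews serious events after each recruitment season (7.7, 7.9). Neither section limits that review to related events.

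The exposed step is therefore expectedness assessment and expedited reporting to the ethics committee, for kinds (b) and (c) only.

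**The case against.** The case against giving this much weight is substantial, and most of it stands as a limit on the consequences.

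- **A site's verdict is not final.** Appendix E does not make the recheck depend on the site having called the event related. This lowers the risk. It does not remove the conflict, because the recheck has no agreed test.
- **The Sponsor can apply the inclusive test.** The Adverse Reaction row says so. But the Serious Adverse Reaction row names only the reporting investigator, and 7.4 works from what was reported as related.
- **The steering committee sees serious events anyway.** A reader might infer that misclassified events would disappear from its view. Sections 7.7 and 7.9 do not support that.
- **Ordinary side effects are outside this route.** A reader might think of routine rash or diarrhoea on antibiotics. Section 7 requires no report form for these when they are non-serious and mild to moderate, and only serious events reach the expectedness step. Section 7 also commits to collecting data on named severe events, with no causality filter stated.
- **Few ambiguous serious events are likely.** The trial plans 108 participants, uses licensed antibiotics, and Section 7 states that irrigation has had no serious side effects reported. This is a fair point about size, though it does not make the definitions compatible.

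The point also touches no estimate, sample size or feasibility conclusion. It is an inconsistency in the safety text.

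**Conclusion.** The conflict is real and is stated in the protocol's own words; it is not detail left to another document. Followed literally, the compulsory definition in 7.2 would exclude from Related some serious events that Section 7 counts as reactions, and those events may miss expedited SUSAR reporting.

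Two stronger readings are tempting and should not be adopted. The first is that all possible reactions would be classed as unrelated: only those with a probable other cause are, while those with a merely reasonable alternative have no category at all. The second is that 7.2 would screen out most possible reactions in this population: the documents contain no rate of serious events and no breakdown by causality, so that proportion is unknown.

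The size cannot be calculated from the documents. The conclusion assumes that assessors apply 7.2 as written and that the Appendix E recheck uses the same definitions. If whoever rechecks in practice uses the Adverse Reaction wording, the loss would be smaller, but nothing in the protocol tells them to. The correction is worth making because it is cheap and concerns safety classification.

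**What to change.** Reconcile the Adverse Reaction row, the Serious Adverse Reaction row and Section 7.2 to one causality threshold, with categories that between them cover every event. The simplest route introduces no new standard and carries the protocol's own Adverse Reaction language into the other two places:

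- Related: a causal relationship with the trial intervention is at least a "reasonable possibility, i.e. the relationship cannot be ruled out".
- Not Related: no reasonable possibility of a causal relationship.
- Serious Adverse Reaction: a serious event that is Related in this sense, in the judgement of the reporting professional or the Sponsor, as the Adverse Reaction row already allows.

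State in Appendix E that the relatedness check uses this definition. Appendix E is a flowchart. The SAE form itself is not in the protocol, so its causality wording should be checked and aligned if it differs.

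The cost is a few lines of text. The one downside is that a few more serious events may go forward to expectedness assessment. No analysis or sample size changes.
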